### **11.12 Missing Data**

Summary statistics and statistical analysis will be based primarily on non-missing values. Sensitivity analyses may be conducted to check the robustness of the analysis results under alternative assumptions with regards to missing data. Further details on the handling of missing values, including rules applied to incomplete questionnaires and any planned sensitivity analyses will be defined in the SAP.

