### **4.2. General Statistical Methods and Data Handling**

#### **4.2.1. General Methods**

Tabulations will be produced for appropriate demographic, baseline, efficacy and safety parameters. For categorical variables, summary tabulations of the number and percentage within each category of the parameter will be presented. Percentages will be calculated based on the number of non-missing values, except if indicated differently. In case of counts equal to zero, reporting will be presented as 0 (with no percentage). For continuous variables, the mean, median, standard deviation, minimum and maximum values will be presented.

For specific categorical efficacy parameters, two-sided 95% confidence interval might be presented.

Formal statistical hypothesis testing will be performed on the primary and secondary efficacy endpoints with all tests conducted at the 2-sided, 0.05 level of significance. Summary statistics will be presented, as well as confidence intervals on selected parameters, as described in the sections below. P-values will be reported with 4 decimals places.

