#### 4.2.7. Missing, Unused, and Spurious Data

In general, there will be no substitutions made to accommodate missing data points. All data recorded on the CRF will be included in data listings that will accompany the clinical study report.

Sensitivity analyses may be performed, and are detailed in the corresponding efficacy endpoint sections.

Clinical laboratory values as “<X” where X is the numerical value of the limit of quantification (LOQ) established by the laboratory will be imputed by LOQ/2 for summaries in the tables.

Clinical laboratory values as “>X” where X is the numerical value of the limit of quantification (LOQ) established by the laboratory will be imputed by LOQ for summaries in the tables.

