#### 4.3.2. Efficacy analysis

At each interim review, summaries by dose group will be provided on the FAS for each of the following:

- Mean daily frequency of moderate and severe HF at baseline, mean daily frequency of moderate and severe HF at each study week, including Week 4 and mean change and percent change from baseline in the mean daily frequency of moderate and severe HF at each study week.
- Mean severity of moderate and severe HF at baseline, mean severity of moderate and severe HF at each study week, including Week 4, and mean change from baseline in the severity of moderate and severe HF at each study week.

If available, summaries of the same data at later time-points (Week 8 and Week 12) will also be reviewed.

Mean daily frequency at each study visit will be calculated using the same method as the one described in section 4.2.11 based on the last 7 days with at least one available data in the evening and/or morning before the corresponding visit.

Mean weekly severity at each study visit will be calculated using the following:

$$\frac{[(\text{number of mild hot flushes for 7 days}) \times 1 + (\text{number of moderate hot flushes for 7 days}) \times 2 + (\text{number of severe hot flushes for 7 days}) \times 3]}{\text{total number of mild, moderate and severe hot flushes over 7 days}}$$

If the number of hot flushes is equal to 0, then the mean severity will be set to 0.

These 7 last days with available data should be within the 14 days prior to the CRF study visit, so in the following window: [CRF Visit date – 14; CRF Visit date], with at least one day within

the last 7 days prior to the study visit. In case of withdrawal, the day this ET visit happened will be checked to see in which windows it is and then to assign the corresponding timepoint. If a CRF visit has already been done at that timepoint, then the CRF visit date will be used. If less than 7 days fulfil these rules, only the correct data will be used in the derivation, and formula will be adjusted using the right number of days as denominator. Morning diary data on the day of a Visit will be included in the derivation as the morning diary is actually associated with the previous calendar day (a complete day is an evening then a morning diary).

In addition, emerging data will be evaluated via the two adaptive following algorithms to evaluate the emerging data at Week 4:

- (i) a Bayesian adaptive Emax (S-shaped) dose-response model fit, and

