#### 4.6.2. Secondary analysis

##### 4.6.2.1. Other hot flush frequency and severity secondary endpoints

The following hot flush frequency and severity secondary endpoints will be summarised by treatment group and scheduled visit (as applicable). In addition, the same approach as for the primary endpoint (MMRM incorporating post-randomization data collected up to treatment discontinuation at week 12) will be used to provide estimates of the change from baseline to weeks 4 and 12.

- Mean change from baseline in mean daily frequency of moderate and severe hot flushes from baseline to Weeks 1, 2, 8 and 16
- Mean change from baseline in mean weekly severity of moderate and severe hot flushes from baseline to Weeks 1, 2, 8 and 16
- Mean change from baseline in mean daily frequency of all hot flushes from baseline to Weeks 1, 2, 4, 8, 12 and 16
- Mean change from baseline in mean weekly severity of all hot flushes from baseline to Weeks 1, 2, 4, 8, 12 and 16
- Mean change from baseline in the mean daily Hot Flush Score (frequency x severity) at Weeks 1, 2, 4, 8, 12 and 16

The above endpoints will be derived using the 7 last days with at least one available data in the evening and/or the morning before the corresponding visit using the same method described in

section 4.2.11. For Week 1, the first 7 post-baseline days with at least one available data in the evening and/or the morning will be used.

The mean change from baseline and the corresponding 95% CI will be displayed graphically by visit on the observed values and by treatment groups.

The proportion of responders, defined as a reduction from baseline of  $\geq 50\%$  and  $\geq 80\%$  on the average mean daily frequency of moderate and severe hot flushes by week will be summarised at each evaluation time.

The proportion of responders will be calculated using the percent change from baseline as below at a visit Week x:

$$\text{Percent change} = (\text{change from baseline in mean daily frequency of moderate and severe HF from baseline to Week } x / \text{Mean daily frequency of moderate and severe HF at baseline}) * 100$$

A subject will be considered as responder with reduction of  $\geq 50\%$  (or  $\geq 80\%$ ) if the percent change is  $\leq -50$  (or  $\leq -80$ ).

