The Week 4 and Week 12 response will be analysed using a logistic regression. The model will be implemented in SAS using the LOGISTIC procedure and will include the responder variables as response variable. The fixed effects in the model will include independent variable of randomized treatment, along with the following baseline covariates: Baseline frequency of moderate and severe HF, Region.

The odds ratio will be used as a measure of association between treatment and response and will be calculated such that an odds ratio  $>1$  is favourable for NT-814. The 95% confidence interval for the odds ratio assumes asymptotic normality of the Wald estimate for the regression coefficient. The Wald p-value associated to the treatment covariate in the logistic regression will be provided. In addition, as a sensitivity analysis, the adjusted relative risk of response will be calculated from a Cochran-Mantel-Haenszel test adjusted on the categorized randomization stratification factor: Region (North America/Europe).

SAS code:

```
PROC LOGISTIC DATA= dataset;
CLASS treat (ref='Placebo') region / param=ref;
MODEL response (event='1') = base treat region;
ODS OUTPUT OddsRatios=OddsRatios_ ParameterEstimates=ParameterEstimates_;
RUN;
* base represents the baseline value of the endpoint;
* response represents the response variable;
* treat represents the treatment group;
* region represents the categorical covariate related to stratification factors;
Further options to control the output may be added.
From ODS OUTPUT, using the correct selection, the outputs will allow getting the
following:
- OddsRatios_: Odd ratio and 95% CI for each treatment
- ParameterEstimates_: p value.

PROC FREQ DATA = dataset;
Tables region*treat*response / cmh;
```

CONFIDENTIAL

```
WHERE treat in ("Placebo","NT-814 40mg");  
RUN;  
* The p-value would be for "Row Mean Scores Differ" in the SAS PROC FREQ output.
```

The following night time awakenings secondary endpoints will be summarised by treatment group and scheduled visit (as applicable). In addition, the same approach as for the primary endpoint (MMRM incorporating post-randomization data collected up to treatment discontinuation at week 12) will be used to provide estimates of the change from baseline to weeks 4 and 12.

- Mean change from baseline in mean daily number of night time awakenings secondary to hot flush at Weeks 1, 2, 4, 8, 12 and 16

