#### 4.6.2.7. Handling of missing data on questionnaires

As MMRM is the main analysis, no handling of missing values will be done. Furthermore, at the time of the BDRM no excessive amount of missing data were observed on the questionnaires, so no imputation rules will be put in place.

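### The Week 4 and Week 12 responder analyses use only subjects with a diary value at that visit, and no planned analysis tests what the missing responses could do

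*SAP*

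**What the plan says.** SAP 4.6.2.1 derives response visit by visit: "The proportion of responders will be calculated using the percent change from baseline as below at a visit Week x". A subject with no value at the visit therefore has no responder status. The analysis is then stated as "The Week 4 and Week 12 response will be analysed using a logistic regression", with the code line "MODEL response (event='1') = base treat region". There is no imputation step, and by default the procedure leaves out a record whose response is missing. The one sensitivity analysis is a Cochran-Mantel-Haenszel relative risk stratified by region, run on the same response variable.

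The general rules point the same way:
- SAP 4.2.1: "Percentages will be calculated based on the number of non-missing values, except if indicated differently".
- SAP 4.2.7: "In general, there will be no substitutions made to accommodate missing data points". It adds that any sensitivity analyses are described in the endpoint sections; the responder section describes none for missing data.
- Protocol 11.12: "Summary statistics and statistical analysis will be based primarily on non-missing values". It leaves further handling to the SAP.

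SAP 4.3.2 sets out when a visit value exists: "These 7 last days with available data should be within the 14 days prior to the CRF study visit". At least one of those days must fall in the last 7, fewer than 7 days are accepted, and early termination diary data go to the window in which that visit falls. SAP 3.2 refers to these rules when it describes the diary days used in the frequency and severity analysis.

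**The concern.** The plan leaves missing data alone throughout. That is reasonable for the MMRM, which keeps subjects with incomplete visits and uses their earlier weeks. The responder models are single-visit models. They drop a subject with no value at that visit, together with anything she showed before it.

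The trial is meant to choose a dose for Phase 3 (Protocol 9.1). Under an observed-case rule the reported response rate of a dose does not depend on how many of its subjects are missing, so a dose that many subjects leave can look as good as one they stay on. Stopping can be linked to treatment: Protocol 9.4.1 provides for withdrawal of the drug when an intolerable event recurs. Protocol 5.1.3 gives a half-life of about 15 to 20 hours, so effect may well fade after stopping, although the documents do not show that it does.

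The plan also does not say whether diary days after stopping study drug count towards response. The MMRM text stops at treatment discontinuation; the responder text is silent. If the same cut-off applies, more responses are missing. If it does not, a value recorded off drug counts as response or non-response for the assigned dose.

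**Working it through.** **The plan's own figures.** No responder rate, responder power or dropout by dose is stated. The nearest figures (Protocol 11.1.1) reproduce. With a difference of 8 − 4 = 4 and SD 4.4, a two-sided t-test at 0.05 has power 0.947 at 32 per group and 0.953 at 33, so N=33 for 95% power is right. The total of 165 is 150 × 1.10. Neither figure concerns the responder endpoint. The 10% allowance is overall.

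**Formula.** Let p be the observed response rate in an arm, m the share missing and q the response rate among the missing. The rate in all FAS subjects is p(1 − m) + qm, so the observed-case rate is too high by m(p − q). This is zero if q = p and largest if q = 0 (missing counted as non-response).

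**Illustration 1.** Assumed observed response is 60% on the dose and 40% on placebo, with q = 0.
- Observed cases: OR = (0.60/0.40)/(0.40/0.60) = 2.25, difference 20 points.
- 10% missing in both arms: 0.60 × 0.90 = 0.54 and 0.40 × 0.90 = 0.36. OR = (0.54/0.46)/(0.36/0.64) = 2.09, difference 18 points.
- 15% missing on the dose, 5% on placebo: 0.60 × 0.85 = 0.51 and 0.40 × 0.95 = 0.38. OR = (0.51/0.49)/(0.38/0.62) = 1.70, difference 13 points.

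**Illustration 2.** This uses the protocol's planning means of 4 and 8 and SD 4.4, with a baseline of 11 per day (midpoint of the 10 to 12 in Protocol Appendix B). A 50% reduction is then 5.5 per day. Treating change as normal:
- Placebo: 1 − Φ((5.5 − 4)/4.4) = 36.7%.
- Top dose: 1 − Φ((5.5 − 8)/4.4) = 71.5%.
- Observed-case OR 4.34, difference 34.8 points, whatever the missing shares.

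With missing counted as non-response, 33 subjects per arm and assumed missing shares:

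| Missing, placebo / dose | Placebo | Dose | Difference (points) | OR | Power, observed cases | Power, non-response |
|---|---|---|---|---|---|---|
| 10% / 10% | 33.0% | 64.4% | 31.4 | 3.67 | 78% | 73% |
| 10% / 20% | 33.0% | 57.2% | 24.2 | 2.71 | 76% | 51% |
| 10% / 30% | 33.0% | 50.1% | 17.1 | 2.04 | 72% | 29% |

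The observed-case dose rate exceeds these by 7.2, 14.3 and 21.5 points. If missing subjects on the dose instead respond at the placebo rate of 36.7%, the excess is 3.5, 7.0 and 10.5 points. For baselines of 10 to 12 the observed rates run from 75.2% to 67.5% on the dose and from 41.0% to 32.5% on placebo, so the pattern does not depend on the choice of 11.

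**The direction is not fixed.** With 10% missing on placebo and none on the dose, non-response counting gives 33.0% and 71.5%, OR 5.10. The observed-case 4.34 is then the smaller figure.

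**The case against.** Several readings go further than the documents allow.

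- A reader might infer that response is measured among completers. It is not. Protocol 7.4 asks that subjects who stop study drug be followed to the end of scheduled visits, partly for efficacy, and the SAP 4.3.2 rules keep partial diaries and in-window early termination data. A subject who stops a dose may still be counted.
- A reader might argue that those who leave cannot have had a sustained reduction. The SAP responder is defined at a single visit, and nothing requires sustained response.
- A reader might call the rates biased without qualification. They are not biased if missing subjects would have responded like those observed. Counting missing as non-response is itself an assumption, and it treats a diary lapse unrelated to the drug as a failure.
- A reader might cite SAP 4.6.2.7, "As MMRM is the main analysis, no handling of missing values will be done". That section concerns questionnaires and does not govern the diary-based responder endpoint. Its remark that blinded review found no excessive missing data likewise covers questionnaires, and not how missing values divide between arms.

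On size, the documents give only a 10% overall allowance, and Protocol 5.1.3 reports all doses well tolerated in post-menopausal women. That study lasted 14 days, so it says little about dropout by dose over 12 weeks, but it gives no ground for presuming a large imbalance.

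On consequence, this is a secondary endpoint. The interim efficacy review uses mean frequency and severity (SAP 4.3), not response. Withdrawals with reasons (SAP 4.4) and adverse events leading to discontinuation (SAP 4.8.2) are tabulated, so a marked imbalance in dropout would be seen. Those tables do not show how many responses are missing at Week 4 or Week 12.

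All of this limits the point. None of it supplies a rule for a missing response or an analysis that tests its effect.

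**Conclusion.** The point holds in a conditional form. By the SAP's own rules the responder analyses are observed-case analyses at each visit, and the only sensitivity analysis shares that feature. If subjects without a value respond less often than those observed, each arm's rate is overstated by m(p − q). The comparison with placebo is inflated mainly when the dose loses more subjects than placebo, and can be understated in the reverse case.

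At the planned 10% in every arm the effect is modest: odds ratio 2.25 to 2.09 in illustration 1 and 4.34 to 3.67 in illustration 2. It becomes material only under imbalances that are assumed here, such as 15% against 5% (2.25 to 1.70). These figures are upper limits in the sense that they take every missing subject as a non-responder.

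A reader might extend the concern to the co-primary results. The documents do not support that: the MMRM uses all weeks to Week 12 and does not drop a subject for lacking a Week 4 or Week 12 value. Which of the two responder analyses should be primary is a matter of judgement. Showing both is a cheap improvement.

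**What to change.** Before unblinding, amend SAP 4.6.2.1 as follows:
1. At Weeks 4 and 12, for the 50% and 80% thresholds, add the same logistic regression on all FAS subjects with a missing response counted as non-response. Report it beside the observed-case model and say in advance which is primary.
2. State whether diary days after stopping study drug count towards response, and whether this matches the MMRM cut-off.
3. Tabulate, by dose and visit, the number of FAS subjects with no responder status, with reasons.

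The cost is a few lines of SAP text, one more model run and one table. Response rates will be lower under non-response counting. Power falls by an amount that depends on dropout: in illustration 2, from 78% to 73% at 10%/10% missing and from 72% to 29% at 10%/30%. Part of that fall reflects the smaller difference that this way of counting defines. Subjects with fewer than 7 days of post-treatment diary data remain outside the FAS under either analysis, so their number by dose should be read alongside.

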
 
Severity of each hot flush recorded on a 3-point scale (mild, moderate or severe)
 
	
 
Mean change from baseline in frequency of moderate and severe hot flushes from baseline to Week 12
 
Mean change from baseline in severity of moderate and severe hot flushes from baseline to Week 4
 
Mean change from baseline in severity of moderate and severe hot flushes from baseline to Week 12
 
 
Secondary Efficacy Endpoints:
 
 
Mean change from baseline in frequency of moderate and severe hot flushes from baseline to Weeks 1, 2, 8 and 16
 
Mean change from baseline in severity of moderate and severe hot flushes from baseline to Weeks 1, 2, 8 and 16
 
Mean change from baseline in frequency of all hot flushes from baseline to Weeks 1, 2, 4, 8, 12 and 16
 
Mean change from baseline in severity of all hot flushes from baseline to Weeks 1, 2, 4, 8, 12 and 16
 
Mean change from baseline in the Hot Flush Score (frequency x severity) at Weeks 1, 2, 4, 8, 12 and 16
 
Responder analyses (proportion of subjects with <math>\geq 50\%</math> and <math>\geq 80\%</math> reductions from baseline in hot flush frequency at Week 12)
 

 
Number of night time awakenings in the diary either due to a hot flush or unrelated to flushing
 
	
 
Mean change from baseline in number of night time awakenings secondary to hot flush at Weeks 1, 2, 4, 8, 12 and 16
 
Mean change from baseline in number of all night time awakenings at Weeks 1, 2, 4, 8, 12 and 16
 

 
Pittsburgh Sleep Quality Index, completed at Baseline and Weeks 4, 8, 12 and 16
 
	
 
Change from baseline in the Global and individual domain scores at Weeks 4, 8, 12 and 16
 

 
Insomnia Severity Index completed at Baseline and Weeks
 
	
 
Change from baseline in the Insomnia Severity Index score at Weeks 4, 8, 12 and 16
 

4, 8, 12 and 16	

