## 10.2 Efficacy assessments

### 10.2.1 Hot Flush Electronic Diary

Subjects will be provided with an eDiary to document the number of hot flushes experienced, the severity of each hot flush using a scale of 1 to 3 (mild, moderate or severe) and the number of night-time awakenings (Appendix C). Subjects will complete the eDiary twice a day, starting the evening of Screening Visit 2 and continuing throughout the study until the final Follow up visit. Each evening, subjects will record the total number of hot flushes of each severity experienced that day since waking. Each morning upon waking, subjects will record the number of times they woke up in the night and the total number of hot flushes of each severity experienced during the night. The severity of each hot flush will be graded by the subject as follows:

Mild: Sensation of heat without sweating

Moderate: Sensation of heat with sweating, but able to continue activity.

Severe: Sensation of heat with sweating, causing cessation (stopping) of activity

A hot flush at night which awakens the subject should be classed as severe. Once awake, subjects should record any further hot flush episodes according to their severity.

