#### Instructions

Please complete this eDiary **twice a day** each day you are in the study (starting the evening of Screening Visit 2).

Each evening, at bedtime, please record the total number of hot flushes of each severity you had during that day since waking. Also, please confirm whether you took your study medication.

Each following morning, upon waking, please record the number of times you woke up in the night, and the total number of hot flushes of each severity you had during the night.

Complete this section in the evening		Complete this section in the morning	
Have you taken your study medication today?	Yes  No 	Total number of times you woke up last night :	 "0" if none
No hot flushes during the day		No hot flushes during the night	
Total number of hot flushes of each severity during the day:		Total number of hot flushes of each severity during the night:	
MILD: Sensation of heat without sweating	 Mild	MILD: Sensation of heat without sweating	 Mild
MODERATE: Sensation of heat with sweating, but able to continue activity.	 Moderate	MODERATE: Sensation of heat with sweating, but able to continue activity.	 Moderate
SEVERE: Sensation of heat with sweating, causing cessation (stopping) of activity.	 Severe	SEVERE: Sensation of heat with sweating, causing cessation (stopping) of activity.	 Severe
		Note: A night-time hot flush that wakes you up (stops you sleeping) is a severe hot flush. If you had more hot flushes once you were awake, record these too.	

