- Mean change from baseline in mean daily number of all night time awakenings at Weeks 1, 2, 4, 8, 12 and 16

The above endpoints will be derived using the 7 last days with at least one available data in the morning before the corresponding visit using the same method than the one described in section 4.2.8.

Night time awakenings secondary to hot flush correspond to severe hot flash recorded on the morning diary, and all night time awakenings correspond to the data recorded in "Total number of times you woke up last night?" field from eDiary recorded in the morning. Number of NTAs secondary to HF can't be higher than number of all NTAs.

The mean change from baseline and the corresponding 95% CI will be displayed graphically by visit on the observed values and by treatment groups.

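### SAP 4.6.2.1 counts every severe flush in the morning diary as an awakening due to a hot flush, including severe flushes that occur once the woman is already awake

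*SAP*

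**What the plan says.** The protocol synopsis describes the assessment as "Number of night time awakenings in the diary either due to a hot flush or unrelated to flushing". Changes from baseline in awakenings secondary to hot flush and in all awakenings are two separate secondary endpoints (Protocol 8.2, SAP 2.5.1.2).

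The awakenings field does not ask for cause. Protocol 10.2.1 says: "Each morning upon waking, subjects will record the number of times they woke up in the night". The other content of the morning entry is the number of night flushes at each severity. The same section sets three rules for severity:

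- the general definition, "Severe: Sensation of heat with sweating, causing cessation (stopping) of activity";
- the night rule, "A hot flush at night which awakens the subject should be classed as severe";
- the rule for a woman already awake, "Once awake, subjects should record any further hot flush episodes according to their severity".

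The eDiary text in Protocol Appendix C repeats the last rule to the subject: "If you had more hot flushes once you were awake, record these too".

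SAP 4.6.2.1 then derives the endpoint: "Night time awakenings secondary to hot flush correspond to severe hot flash recorded on the morning diary". It takes all awakenings from the awakenings field and adds: "Number of NTAs secondary to HF can't be higher than number of all NTAs". No action is given for a night on which the entries break that limit.

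**The concern.** The night rule makes every waking flush severe. It does not make every severe night flush a waking one. A flush while awake is severe if it brings sweating and stops activity, and the diary asks for it to be entered. The derivation therefore mixes two kinds of event under a name that fits only one, and the SAP states as a fact a limit that its own derivation does not guarantee.

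The endpoint gets MMRM estimates at Weeks 4 and 12, and SAP 4.2.1 tests secondary efficacy endpoints at the two-sided 0.05 level. If treatment reduces severe flushes while awake, the endpoint as derived would report that as fewer awakenings. The same severe flushes also enter the co-primary frequency, so the result would be weaker separate evidence on sleep than its name suggests.

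**Working it through.** The documents give no sample size, power or expected value for this endpoint, so there is no planned figure to reproduce. The check is bookkeeping for a single night.

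**Quantities**, following Protocol 10.2.1 and SAP 4.6.2.1:

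- h = awakenings caused by a flush (each also adds one severe flush)
- o = awakenings from other causes
- s = severe flushes while already awake
- S = h + s, the SAP's value for awakenings secondary to hot flush
- A = h + o, all awakenings

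**Results**

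- Over-count: S − h = s.
- The limit is broken when S > A, that is, when s > o.
- If the night is capped at A, the remaining over-count is min(S, A) − h = min(s, o).

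| Night | h | o | s | S | A | S > A? | min(S, A) | Over-count, uncapped | Over-count, capped |
|---|---|---|---|---|---|---|---|---|---|
| (a) | 1 | 0 | 1 | 2 | 1 | yes | 1 | 1 | 0 |
| (b) | 2 | 1 | 2 | 4 | 3 | yes | 3 | 2 | 1 |
| (c) | 1 | 2 | 2 | 3 | 3 | no | 3 | 2 | 2 |
| (d) | 0 | 1 | 1 | 1 | 1 | no | 1 | 1 | 1 |

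Night (a) breaks the limit with a fully compliant diary. Nights (c) and (d) respect the limit and are still wrong. In night (c), removing the two awake flushes lowers the endpoint from 3 to 1, capped or not, while flush awakenings stay at 1 and all awakenings at 3.

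**Per night or on the mean.** Take two nights with severe counts 3 and 0 and awakenings 1 and 2. Both means are 1.5, so a cap on the mean leaves (3 + 0)/2 = 1.5. A nightly cap gives (1 + 0)/2 = 0.5. Two programmers could each respect the SAP's sentence and report different values. For its method, SAP 4.6.2.1 points to section 4.2.8, which defines Study Day. Section 4.2.11, which defines the diary averages, has no rule on this either.

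**Illustration only; every rate is assumed.** Let h be Poisson with mean 1 to 3 per night, o Poisson with mean 0.5 to 1.0, and let each awakening bring 0.05 to 0.5 severe awake flushes on average. The mean over-count is that rate times the mean of h + o: from 0.05 × 1.5 = 0.075 to 0.5 × 4 = 2.0 per night. In simulation over this grid, the limit was broken on about 2% to 63% of nights, and a nightly cap left a mean over-count of about 0.04 to 0.8. The width of these ranges shows that the documents do not fix the size.

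**The case against.** The strongest reply is that the limit may already be a rule. The sentence directly follows the derivation and can be read as an instruction to the programmer. If it is a cap, reported values would not exceed all awakenings. This is fair, and a reader who infers that reported values will exceed their parent count goes further than the text allows. What stands is that the SAP does not say how the limit applies, and that a cap still leaves nights (b), (c) and (d) over-counted.

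Four further inferences are tempting but not supported:

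- *The treatment effect is biased.* The documents give no rate of severe flushes while awake in any group, so neither the size nor the direction of an effect on the contrast with placebo is shown. Nor do they show which women would be affected most.
- *This is the only endpoint that ties flushes to sleep.* It is not. HFRDIS item 4 asks about flush interference with sleep, and SAP 4.6.2.4 summarises each item and applies the MMRM approach.
- *The diary cannot record cause.* Appendix C says its versions are for reference and may differ slightly from those used, and the synopsis describes a split by cause. It is safe to say only that the layout shown has no such item.
- *The main conclusions are at risk.* The endpoint is not a co-primary, and SAP 4.3 limits interim efficacy review to flush frequency and severity. All awakenings are analysed by the same approach, so a fall only in severe awake flushes should show as a discrepancy between the two results.

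These points limit the importance of the problem. They do not make the derivation correct.

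**Conclusion.** The concern holds as a derivation and labelling fault in one secondary endpoint. The morning severe count equals awakenings due to flushes only if no severe flush occurs while awake at night; otherwise it is too high by the number of such flushes. It can exceed total awakenings, and the SAP's sentence on that limit is open to at least three readings (assumption, check or cap) and two levels of application (night or mean).

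The conclusion assumes that women follow the diary instructions and that the diary used matches the layout shown. It needs no assumed rate. The size of the over-count and any effect on the comparison with placebo remain unknown. The SAP should be corrected because it states a rule that gives a wrong value in ordinary, compliant cases, and the correction is cheap.

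**What to change.** In SAP 4.6.2.1:

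1. For each night, derive the minimum of severe flushes in the morning entry and total awakenings in the same entry. Then average over the 7 days. Apply this at baseline and at all visits.
2. Count the severe field as 0 when the woman has marked that she had no flushes that night. Set the night to missing only when the severe count or the awakenings count is truly absent. Otherwise flush-free nights, which are the best outcomes, could be dropped.
3. Label the result an upper bound on flush-related awakenings. In a compliant diary flush awakenings cannot exceed either field, so the bound is valid, but the cap removes only the excess above total awakenings.
4. Report the uncapped count under its own name, severe night-time hot flushes.
5. State that a fall in either measure will not be interpreted as fewer flush-related awakenings without reference to the all-awakenings result.
6. Replace the sentence on the limit with the nightly rule, and correct the reference to section 4.2.8.

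The cost is a short change to the derivation, using two fields already collected, and one extra label in the outputs. The downside is that over-counting of min(s, o) per night remains, because the layout shown does not ask the cause of an awakening.
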